
the results of that study.²² In the experience of 20 patients treated in cohort 4, 10 have had toxicity that precluded finishing 12 weeks of therapy, suggesting that for patients with resected stages 3C and 4 melanoma, the regimen of ipilimumab at 3 mg/kg and NIVOLUMAB at 1 mg/kg every 3 weeks for 4 doses may be difficult to tolerate, and suggesting that an alternative regimen of ipilimumab at 1 mg/kg and NIVOLUMAB at 3 mg/kg every 3 weeks for 4 doses was worthy of testing in cohort 5 at Moffitt. In that experience, 17 of the 20 patients treated were able to continue past the 12-week combination period. In that cohort, treatment was for 2 years with nivolumab alone after the 12-week induction with nivolumab and ipilimumab²³. In the current protocol, an additional 20 patients will be treated with the same doses as cohort 5 at Moffitt (ipilimumab 1/nivolumab 3) and the total duration of nivolumab treatment alone will be 1 year, in order to gather further feasibility and toxicity experience with this adjuvant regimen.

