2.2. Primary Endpoint

The primary efficacy analysis is time to relapse. Time to relapse will be summarized using descriptive statistics. Scanning and exams to detect recurrence will be conducted every 3 months until 2 years from finishing treatment, then every 6-12 months (minimum of every 12 months) for 2 years, then yearly thereafter.

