3.1. Inclusion Criteria

Subjects must meet the following criteria at Screening to be eligible to participate in the study.

1. Be at least 16 years of age;
2. Histologic diagnosis of resected Stages IIIB/IIIC/ IV melanoma, with no evidence of disease clinically and radiologically, and negative surgical margins. All melanomas regardless of primary site of disease will be allowed;
3. Eastern Cooperative Oncology Group (ECOG) performance status score of 0 or 1 (Appendix 2);
4. Prior chemotherapy or immunotherapy (tumor vaccine, cytokine, or growth factor given to control the cancer) must have been completed at least 4 weeks before study drug administration, and all adverse events have either returned to baseline or stabilized;

5. Prior treated brain or meningeal metastases must be without magnetic resonance imaging (MRI) evidence of progression for at least 8 weeks and off immunosuppressive doses of systemic steroids (> 10 mg/day prednisone or equivalent) for at least 2 weeks before study drug administration;
6. Prior systemic radiation therapy must have been completed at least 4 weeks before study drug administration. Prior focal radiotherapy completed at least 2 weeks before study drug administration. No radiopharmaceuticals (strontium, samarium) within 8 weeks before study drug administration;
7. Immunosuppressive doses of systemic medications, such as steroids or absorbed topical steroids (doses > 10 mg/day prednisone or equivalent) must be discontinued at least 2 weeks before study drug administration;
8. Completed nitrosourea treatment at least 6 weeks before administration of any study drug;
9. Prior surgery that required general anesthesia must be completed at least 4 weeks before study drug administration. Surgery requiring local/epidural anesthesia must be completed at least 72 hours before study drug administration and subjects should be recovered;
10. Screening laboratory values must meet the following criteria:
 - white blood cells (WBCs) ≥ 2000 cells/ μ L
 - neutrophils ≥ 1500 cells/ μ L
 - platelets $\geq 100 \times 10^3/\mu$ L
 - hemoglobin ≥ 9.0 g/dL
 - serum creatinine ≤ 2 mg/dL
 - AST ≤ 2.5 x upper limit of normal (ULN) without, and ≤ 5 x ULN with hepatic metastasis
 - ALT ≤ 2.5 x ULN without, and ≤ 5 x ULN with hepatic metastasis
 - bilirubin ≤ 2 x ULN (except subjects with Gilbert's syndrome, who must have total bilirubin < 3.0 mg/dL)

11. Females of childbearing potential must:

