The four single nucleotide polymorphisms known to be present in CTLA-4 (79-81) and at least six known for PD-1 (82, 83) will be measured by DNA PCR analysis, and a selection of 20% of the total samples will have the results verified by direct DNA sequencing of the relevant areas of DNA. All subjects will be used from the first, and the second trials and the data will be pooled to allow correlations, if any, to be drawn between the presence of a SNP, response, time to progression and development of autoimmunity.

Studies on Regulatory T cells

We propose to study the regulatory activity of CD4⁺CD25⁺ ^{high} cells before and after NIVOLUMAB +ipilimumab treatment. Peripheral blood CD4⁺ T cells will be sorted into CD4⁺CD25⁺ and CD4⁺CD25⁻ populations by flow cytometry. The latter cell subset (responders) will be stimulated with anti-CD3 (10 µg/ml) alone or with anti-CD28 (2µg/ml) and with or without IL-2 (10 IU/ml) in the presence of increasing numbers of sorted CD4⁺CD25⁺ cells. In addition, CD4⁺CD25⁻ will be stimulated with allogeneic mature myeloid dendritic cells (DC), generated from PBMC with GM-CSF and IL-4 and matured with a cytokine cocktail (IL-6, IL-1 beta, TNF-alpha and PGE-2), in the presence or absence of

CD4⁺CD25⁺. The ability of CD4⁺CD25⁺ to suppress the proliferation of CD4⁺CD25⁻ to polyclonal or allogeneic stimulation in a 3 to 5 day proliferation assay using tritiated thymidine incorporation will be determined. We anticipate that CD4⁺CD25⁺ cells will exhibit suppressor activity in vitro as has been previously described and that NIVOLUMAB + ipilimumab treatment will inhibit their suppressive activity in either polyclonal or allogeneic proliferation reaction. We will examine whether loss of suppressor activity of CD4⁺CD25⁺ cells, if found, following NIVOLUMAB + ipilimumab treatment correlates with the development of colitis or other autoimmune side effects. The suppression of allo MLR proliferation by isolated CD4⁺CD25⁺ is an established assay, and well-established in the principal investigator group.

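### The Appendix 4 SNP analysis pools two unnamed trials without stratifying by trial or regimen, and its efficacy outcomes are not this trial's endpoints

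*Combined protocol and SAP*

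**What the plan says.** The Polymorphism Analysis paragraph of Appendix 4 covers "The four single nucleotide polymorphisms known to be present in CTLA-4 (79-81) and at least six known for PD-1", so at least 4 + 6 = 10 SNPs. On the data set it says: "All subjects will be used from the first, and the second trials and the data will be pooled to allow correlations". The correlations are to be "drawn between the presence of a SNP, response, time to progression and development of autoimmunity".

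The paragraph does not say which trials these are, which regimens they used, how the outcomes are defined, or whether trial or regimen enters the analysis. Section 6 does not mention SNPs. The paragraph cites reference numbers 79 to 83, but the list in section 13 ends at 23.

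Elsewhere the plan is clear about this trial's population and endpoints. Inclusion criterion 2 in section 3.1 requires resected melanoma "with no evidence of disease clinically and radiologically, and negative surgical margins". Section 2.2 states: "The primary efficacy analysis is time to relapse". Section 5.4 defines efficacy as relapse-free survival, and section 2.3 adds overall survival. Sections 6.3.3 and 6.10 define the irAE.

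**The concern.** There are two separate weaknesses.

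- **Pooling.** Sections 1.4 to 1.4.3 describe earlier experience with nivolumab plus a peptide vaccine, with ipilimumab 3 mg/kg plus nivolumab 1 mg/kg, and with ipilimumab 1 mg/kg plus nivolumab 3 mg/kg. Tolerability differed. In cohort 4 of the predecessor trial, of 20 patients "10 have had toxicity that precluded finishing 12 weeks of therapy"; in cohort 5, 17 of 20 continued past week 12. Nivolumab alone then ran for 2 years in cohort 5, against 48 weeks here, so the time at risk for immune toxicity also differs. If such groups are merged and a SNP is more common in one of them, that SNP appears linked to toxicity even if it has no effect within any regimen.
- **Outcomes.** For patients with no evidence of disease, tumour response is not an endpoint, time to progression is not the term used for the efficacy endpoint, and autoimmunity is not tied to the defined irAE. An analyst would have to choose definitions after seeing the data.

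At stake is the credibility of any reported genetic marker of immune toxicity or relapse. No primary or secondary objective depends on it.

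**Working it through.** The plan gives no sample size, effect size or error rate for the SNP analysis, so there is no figure to reproduce. The check asks how far crude pooling can mislead when a SNP has no effect within either regimen.

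**Inputs**
- Event proportion in group 1: 10/20 = 0.50 (section 1.4.3, cohort 4, toxicity precluding completion of 12 weeks).
- Event proportion in group 2: (20 − 17)/20 = 0.15 (section 1.4.3, cohort 5, did not continue past 12 weeks). The protocol gives no reason for these 3, so 0.15 stands in for a toxicity rate.
- Group size: 20 each.
- Carrier frequencies f1 and f2: not in the documents; assumed over 0.20 to 0.60.

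**Formula**
- Carriers: c = 20(f1 + f2), with events a = 20(0.50·f1 + 0.15·f2).
- Non-carriers: d = 40 − c, with events b = 20[0.50(1 − f1) + 0.15(1 − f2)].
- Crude odds ratio = [a/(c − a)] / [b/(d − b)]. Within each group the true odds ratio is 1.00.

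Example, f1 = 0.50 and f2 = 0.30: a = 5.0 + 0.9 = 5.9 of 16; b = 5.0 + 2.1 = 7.1 of 24; odds ratio = (5.9/10.1)/(7.1/16.9) = 1.39.

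| f1 / f2 | Carriers with event | Non-carriers with event | Crude odds ratio | Crude test, type I error |
|---|---|---|---|---|
| 0.30 / 0.30 | 3.9 of 12 | 9.1 of 28 | 1.00 | about 5% |
| 0.40 / 0.30 | 4.9 of 14 | 8.1 of 26 | 1.19 | about 6% |
| 0.50 / 0.30 | 5.9 of 16 | 7.1 of 24 | 1.39 | about 8% |
| 0.50 / 0.20 | 5.6 of 14 | 7.4 of 26 | 1.68 | about 12% |
| 0.60 / 0.20 | 6.6 of 16 | 6.4 of 24 | 1.93 | about 17% |

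The last column is simulated (20 per group, chi-square test at two-sided 0.05). The Mantel-Haenszel test stratified by group stays at about 5% in every row.

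**Sensitivity**
- The bias can go either way. With f1 = 0.20 and f2 = 0.50, a = 3.5 of 14 and b = 9.5 of 26, so the odds ratio is (3.5/10.5)/(9.5/16.5) = 0.58.
- If none of the 3 cohort 5 patients stopped for toxicity, the second proportion is 0. At 0.50/0.30 the odds ratio is then (5/11)/(5/19) = 1.73, and at 0.60/0.20 it is (6/10)/(4/20) = 3.00.
- If the pooled groups have the same event proportion, the crude odds ratio is 1.00 whatever the carrier frequencies.

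**The case against.** The strongest reply is that this is one exploratory appendix paragraph, probably carried over from another protocol, and that the defects are loose wording. Much of that stands.

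- **Unnamed trials.** Which regimens, centres or disease states would be merged is an inference from sections 1.4 to 1.4.3. The 10/20 against 17/20 contrast is between two cohorts of one predecessor trial, and this trial uses cohort 5's induction doses. If only those two were pooled, the toxicity contrast could be small.
- **A germline SNP is not changed by treatment.** A reader might infer that pooling makes the associations confounded as such. It does not. If underlying carrier frequencies are equal, chance imbalance is already covered by the nominal error rate, as the first row of the table shows.
- **The outcomes are not impossible.** A reader might infer that response and time to progression cannot be scored in disease-free patients. The footnotes to Table 1 provide for re-imaging until progression and for recording its date and site, so time to progression can be read as time to relapse. Sections 5.6.3 and 6.3.4 classify T-cell proliferation as response or non-response. Autoimmunity can plainly occur in these patients. If one pooled trial enrolled patients with measurable disease, tumour response would exist there.
- **Multiplicity.** A reader might count 10 SNPs by 3 outcomes as 30 tests and quote 1 − 0.95^30 = 0.79 as the chance of a false positive. That needs 30 independent tests at 0.05. The appendix specifies correlations rather than tests, the SNPs lie in two genes, and response and progression are related.

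What the reply leaves untouched is that the paragraph gives no trial names, no outcome definitions and no handling of trial or regimen, and no other section supplies them.

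**Conclusion.** The point holds as a conditional risk and a specification gap. The stated rule is pooling with no separation by trial or regimen, and the efficacy outcomes do not match time to relapse/RFS in patients who enter disease-free. Bias in a SNP-toxicity association requires both a regimen difference in toxicity, which the earlier cohorts suggest, and a systematic difference in carrier frequency, on which the documents are silent. For assumed gaps of 10 to 40 percentage points, the spurious odds ratio runs from about 1.2 to 1.9 and crude type I error from about 6% to 17%; with no gap there is no bias. These sizes rest on two cohorts of 20 and on treating 3/20 as toxicity. They do not describe the actual trials to be pooled. The documents do not support saying that the associations are confounded, or that the outcomes do not exist. The trial's objectives are unaffected. This is a cheap improvement.

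**What to change.** Revise the Polymorphism Analysis paragraph of Appendix 4 as follows, and cross-refer to it from section 6.3.4.

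1. Name the trials, cohorts and regimens to be pooled.
2. Replace time to progression with time to relapse/RFS, and autoimmunity with the irAE as defined in sections 6.3.3 and 6.10.
3. Drop tumour response, or state that response means the T-cell proliferation response. In the latter case point to one definition, because section 6.3.4.1 uses CD107a-positive and Appendix 4 tetramer-positive CD8+ cells.
4. Stratify each SNP association by trial and regimen: for example a Mantel-Haenszel or exact stratified odds ratio for irAE, and a stratified log-rank test for RFS.
5. Report estimates with confidence intervals and label the analysis hypothesis-generating. A false-discovery-rate adjustment across SNPs is optional.

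The cost is a few sentences of text, with no new patients, samples or visits. Intervals will be somewhat wider. With about 20 subjects per stratum, a SNP carried by 30% gives only 6 carriers per stratum, so some strata will be sparse. That loss of precision has not been quantified here.
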